### **Obtaining the smallest worthwhile effect (SWD)**

The SWD will be estimated using the Benefit-Harm Trade-off Method (BHTM) (Barrett et al., 2005), presenting the survey respondents with variable, hypothetical magnitudes of antidepressant outcomes to find the smallest acceptable effect over natural recovery. The overall average smallest acceptable effect represents the SWD. Respondents will be asked a series of questions regarding the percentage of improvement they consider to be worthwhile, given the costs of antidepressant treatment. We will use the selective serotonin reuptake inhibitors (SSRIs) and serotonin-norepinephrine reuptake inhibitors (SNRIs) as the exemplar cases in the descriptions of antidepressants, as they are the most frequently prescribed (Luo et al., 2020), have similar efficacy and harm profiles (Cipriani et al., 2018), and are now mostly off-patent and hence similarly inexpensive.

The BHTM is a two-step method. In Step 1, respondents are presented with summaries of clinical depression, benefits, and costs (side effects, expenses, and burdens) associated with antidepressant treatment and with no treatment/natural recovery (see Supplement 2). The summaries will be piloted using two members of the Patient and Public Involvement (PPI) group at Oxford University. The patient members will review the scripts and provide valuable feedback as to the clarity, inclusivity, and accuracy of patient experiences captured by the descriptions. Respondents will be informed about how much improvement can be expected without antidepressant treatment, i.e., natural recovery. After the no-treatment comparison is established, respondents are presented with the potential costs of antidepressant treatment. They will be provided with a list of common (Trindade et al., 1998; U.S. Food and Drug Administration, 2019) and rare side effects (U.S. Food and Drug Administration, 2019).

In Step 2, respondents will determine if antidepressants are worthwhile given a hypothetical symptom reduction percentage compared to the known symptom reduction of natural recovery. They are asked to weigh the cost and benefits and asked if they would take the drug alternating between variable magnitudes of hypothetical

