### Sample Size

Sample size was calculated to achieve expected precision in the estimates of the SWD. Because there has been no study to estimate SWD for depression and its SD is unknown, we substituted it with the SD of SWD for pain also measured on a scale of 0-100: this study suggested an SD of 22 for SWDs of 20% (Ferreira et al., 2013). Assuming a similar SD, and to obtain a 95% confidence interval within 10 points, approximately 80 respondents per group are needed. We will also randomly assign participants to either the *high-to-low* or *back-and-forth* BHTM methods, which will require twice the respondents per method to determine differences between the methods with 160 respondents per group (80 respondents x 2 methods). Since we are estimating SWD and its 95% CI for 4 subgroups (see respondent recruitment above), 640 respondents are needed (160 respondents x 4 groups). This should be enough to examine all the pre-specified potential predictors (see Data analysis below) (Austin & Steyerberg, 2015).

The survey will be piloted with 300 respondents to determine if the population distribution estimate is appropriate to reach  $n = 160$  in all four subgroups. We have estimated that approximately 20% of the respondents will screen positive for moderate to severe depressive symptoms with the PHQ-9. This is greater than the general population, but still a conservative estimate for MTurk subgroups, which have been shown to demonstrate up to 3.6 times greater depression point prevalence than the general population (Ophir et al., 2020). Based on this estimated MTurk-specific subgroup populations, approximately 1,600 respondents may be necessary to reach 80 in the subgroups with the smallest populations (see Figure 1). If more respondents are needed, recruitment will continue until 80 people per subgroup are reached.

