**Responses follow one of two different randomly assigned algorithms presented in Supplement 4.**

**Supplement 4. Question Sequence Algorithms**  
**4a. Back-and-Forth Benefit Harm Tradeoff Method**

[figure not shown]
4b. High-to-Low Benefit Harm Tradeoff Method

- Yes, it is worthwhile
- No, it is not worthwhile

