**Supplement 5. Benefit-Harm Tradeoff Method Algorithm Testing and Sample Size Calculation**

We used two separate methods within the BHTM for determining the participants' SWD: the *high-to-low* method and the *back-and-forth* method (see Supplements 3 and 4). Both methods have been employed in the SWD literature (See Ferreira et al., 2012 and McNamara et al., 2015), and the most accurate SWD estimation had not been determined. Therefore, we opted to randomly allocated participants 1:1 to each method to see if they differed in their estimation. Our original sample size estimate for the SWD and its 95% CI for 4 clinical subgroups, required 780 participants based on population estimates. However, testing the difference between two separate methods required double the estimate. Based on subgroup populations, approximately N=1,600 participants were thought to be necessary to reach a minimum of n=80 in all 8 subgroups.

After we reached a minimum number of participants per group, we compared the SWD between methods. We found the difference between methods was 3.6 percentage points and we used 5 percentage point increments for the SWD. Thus, we determined both methods to be equally appropriate and all participants were analyzed together. Recruitment was stopped after all subgroups included n=80.

**Supplement 6.** Associations between demographic and clinical variables and SWD

	Univariable regression		Multivariable regression	
	Coefficient	95%CI	Coefficient	95% CI
Demographic Variables				
Age	0.050	-0.021 to 0.12	0.069	-0.03 to 0.16
Sex				
Male	ref		ref	
Female	-0.61	-2.75 to 1.53	-1.66	-4.01 to 0.67
Non-binary	1.66	-7.23 to 10.56	1.43	-7.75 to 10.61
Race				
White/Caucasian	ref		ref	
Black/African American	2.22	-2.53 to 6.97	3.57	-1.29 to 8.43
Asian	2.74	-2.40 to 7.89	3.33	-2.06 to 8.71
Latino/Hispanic	3.69	-1.98 to 9.35	6.55	0.62 to 12.47
Multiracial	2.27	-4.45 to 8.90	3.71	-3.00 to 10.42
Other	1.42	-8.86 to 11.70	0.90	-9.40 to 11.19
Education				
Less than high school	3.78	-2.36 to 9.92	2.61	-3.74 to 8.94
High school graduate/Equivalent	0.36	-2.96 to 3.69	0.04	-3.35 to 3.44
Some college	-0.61	-3.18 to 1.96	-1.16	-3.87 to 1.54
2-year degree	-3.23	-6.56 to 0.10	-2.76	-6.15 to 0.63
4-year degree	ref		ref	
Master's degree	-0.86	-4.45 to 2.73	-1.74	-5.34 to 1.86
Doctorate	-4.04	-11.25 to 3.17	-4.09	-11.26 to 3.08
Employment				
Disabled	3.62	-0.36 to 7.60	4.08	-0.23 to 8.40

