**Supplement 7. Conversion of the SWD into OR and SMD**

An RR can be converted into a corresponding OR, given the control event rate (CER), by the following formula:

$$\text{OR} = \text{RR} * (1 - \text{CER}) / (1 - \text{RR} * \text{CER})$$

When CER=0.30 and SWD=0.20, RR=0.50/0.30=1.67 and OR=2.33.

Or when CER=0.30 and SWD=0.25, RR=0.55/0.30=1.83 and OR=2.85.

OR can be converted into SMD using Chinn's formula :

$$\text{SMD} = \text{sqrt}(3) * \text{Ln}(\text{OR}) / \pi = 1.81 \text{ Ln}(\text{OR})$$

Then OR of 2.33 corresponds with SMD of 0.47, and OR of 2.85 corresponds with SMD of 0.58.

1. Chinn S. A simple method for converting an odds ratio to effect size for use in meta-analysis. *Stat Med* 2000;19(22):3127-31.

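### If each respondent is scored at the lowest accepted level on a 5-point grid, the SWD is rounded upward (by about 2.5 points on average if thresholds are evenly spread), and no midpoint or interval-censored estimate is given beside it

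*Combined protocol and SAP*

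**What the plan says.** The protocol section on obtaining the SWD describes a search "to find the smallest acceptable effect over natural recovery" and then defines the estimate: "The overall average smallest acceptable effect represents the SWD". Supplement 5 states that "we used 5 percentage point increments for the SWD". It uses that step only to judge that a 3.6-point difference between the two question sequences is unimportant.

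The script in Supplement 3 opens at 100/100 feeling much better, against 30/100 untreated, and goes on to other levels only after a yes. After that, "Responses follow one of two different randomly assigned algorithms presented in Supplement 4".

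The Data analysis section treats the SWD as continuous and summarises it by mean and SD, or by median and IQR if it is skewed. Supplement 7 converts two values, 20 and 25 points, to an OR and then an SMD. For the first it writes "When CER=0.30 and SWD=0.20, RR=0.50/0.30=1.67 and OR=2.33", with SMD 0.47; for the second it gives OR 2.85 and SMD 0.58.

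Nothing in the readable text mentions midpoints, interval censoring or error from the grid.

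**The concern.** A yes/no answer at fixed levels does not reveal a threshold. It brackets one. If the levels are 5 points apart and the score is the lowest level accepted, a score of 20 says that 20 was accepted and 15 was not. The threshold is then somewhere above 15 and no higher than 20. Averaging the upper ends of such brackets as if they were exact puts all the rounding error on one side.

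The SWD is offered as a yardstick for present and future antidepressants, and Supplement 7 carries it to two decimals of SMD. An upward rounding error raises that yardstick. Unlike sampling error, it does not shrink with recruitment, and the confidence interval does not show it.

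**Working it through.** **Inputs.** Step: 5 points (Supplement 5). Planning SD: 22, from the Sample Size section ("this study suggested an SD of 22 for SWDs of 20" percent, borrowed from a pain study). Sample sizes: 80 and 160 per group and 640 in total (Sample Size); about 1,600 (Sample Size and Supplement 5). Control event rate: 0.30 (Supplement 7). The position of thresholds inside each step is not given in the documents and has to be assumed.

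**The plan's own precision figure.** The protocol says "to obtain a 95% confidence interval within 10 points, approximately 80 respondents per group are needed". Taking 10 as the total width, n = (1.96 × 22 / 5)² = 74.4, so 75 (77 with the t distribution). The stated 80 is a slightly generous rounding: 1.96 × 22 / √80 = 4.82, a width of 9.64. The total of 160 × 4 = 640 is exact.

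**Sampling error, 1.96 × 22 / √n.**

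| n | 95% half-width (points) |
|---|---|
| 80 | 4.82 |
| 160 | 3.41 |
| 640 | 1.70 |
| 1,600 | 1.08 |

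Supplement 6 gives a check that does not need the borrowed SD. The univariable interval for lifetime depression, -2.85 to 1.17, implies an SE of 4.02 / (2 × 1.96) = 1.03 for a two-group difference. With a common SD, the SE of the pooled mean is at most half of that, about 0.51, which gives a half-width of at most about 1.0.

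**Grid error, if the score is the lowest accepted level.** Score minus threshold = 5 × ceil(t/5) - t, which runs from 0 to just under 5.

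- Thresholds spread evenly within steps: mean excess 5/2 = 2.5. Simulated thresholds between 0 and 70 gave 2.50 (uniform), 2.53 (normal, mean 20, SD 22, truncated) and 2.67 (gamma with the same mean and SD, truncated).
- A share h of thresholds exactly on grid values: mean excess about 2.5 × (1 - h). That is 1.25 at one half, 0.62 at three quarters and 0.25 at 90%.
- Median reported: the excess is the distance from the true median to the reported grid value, anywhere from 0 to under 5.

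**Comparison.** An excess of 2.5 is 2.5 / 1.70 = 1.5 times the pooled half-width at N=640 and 2.5 / 1.08 = 2.3 times at N=1,600. The break-even excess, as a share of the step, is 1.70 / 5 = 34% and 1.08 / 5 = 22%. With half the thresholds on grid values, 1.25 still exceeds 1.08 but not 1.70.

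**Effect on Supplement 7.** OR = [(0.30 + s) / (0.70 - s)] / (0.30 / 0.70) and SMD = √3 × ln(OR) / π. (√3/π is 0.551, so the printed 1.81 works as a divisor. The printed SMDs are consistent with that.)

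| s | OR | SMD |
|---|---|---|
| 0.150 | 1.91 | 0.36 |
| 0.175 | 2.11 | 0.41 |
| 0.200 | 2.33 | 0.47 |
| 0.225 | 2.58 | 0.52 |
| 0.250 | 2.85 | 0.58 |

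The rows for 0.20 and 0.25 reproduce the plan. With no assumption about spread, a score of 20 covers SMD 0.36 to 0.47. At the midpoints, 20 becomes SMD 0.41 and 25 becomes 0.52.

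**The case against.** The strongest objection is that the scoring rule is inferred. Supplement 5 describes the increments of the recorded SWD, not the spacing of the questions, and the value assigned at the end of each path is in the Supplement 4 charts, which were not available to this review. Their absence here is not a fault in the plan. A 5-point scale might also arise from questions 10 points apart with the midpoint assigned, and the average bias would then be near zero.

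That alternative fits the text poorly. Starting from 100/100 against 30/100, levels 10 points apart have midpoints at 65, 55, and so on down to 25, 15 and 5. Those values move in steps of 10 and never include 20, which Supplement 7 uses. The wording in the protocol also points to the lowest accepted level. The alternative is unlikely but not excluded, so the conditional wording stays. A reader holding the charts can settle it directly.

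Two further objections stand and limit the size:

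- People often think in round numbers. Anyone whose threshold is exactly on a grid value has no error, so 2.5 is an assumption and heaping lowers it.
- The plan allows a median, and the 2.5 average and the SD/√N comparison apply only to a mean.

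It can also be said that Supplement 5 discloses the 5-point resolution and that Supplement 7 is a worked example at two values one step apart. Both are true, but neither shows the direction of the error or gives an estimate free of it.

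**Conclusion.** The point holds conditionally. If the score is the lowest accepted level on a 5-point grid, as the readable text indicates, the error is upward only and under 5 points per person. For a mean it averages about 2.5 points under an even spread and about 1.25 if half the thresholds sit on grid values. At 2.5 it is larger than the pooled 95% half-width at both 640 and 1,600 respondents.

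A reader might infer more: that every respondent and every subgroup is overstated by 2.5 points, that the subgroup findings are distorted, or that the headline SWD is known to be wrong by that amount. The documents do not support this. The scoring rule is not confirmed, the spread within steps is unknown, and the summary may be a median. The plan sets its precision per group, and 2.5 lies inside the half-widths of 4.8 and 3.4. A shift common to all groups largely cancels in the Supplement 6 contrasts, and in the comparison of the two question sequences if both use the same rule.

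This is a worthwhile, inexpensive improvement to how the estimate is reported. It does not invalidate the study.

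**What to change.** In Data analysis, state the value assigned at the end of each question path. Where it is the lowest accepted level, treat each answer as lying between the highest rejected and the lowest accepted level. Report an interval-censored estimate (parametric or nonparametric), or at minimum one based on interval midpoints, beside the lowest-accepted-level figure. Show both in Supplement 7, so that the OR and SMD carry the same range.

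The cost is some plan wording and one extra analysis of data already held. The downside is a headline figure lower by up to about 2.5 points if a mean is reported.

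Respondents who refuse even at 100/100 are a separate matter. Supplement 2 already provides sensitivity analyses that include them, and this change does not touch that.

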**Supplement 7. Conversion of the SWD into OR and SMD**

An RR can be converted into a corresponding OR, given the control event rate (CER), by the following formula:

$$\text{OR} = \text{RR} * (1 - \text{CER}) / (1 - \text{RR} * \text{CER})$$

When CER=0.30 and SWD=0.20, RR=0.50/0.30=1.67 and OR=2.33.

Or when CER=0.30 and SWD=0.25, RR=0.55/0.30=1.83 and OR=2.85.

OR can be converted into SMD using Chinn's formula :

$$\text{SMD} = \text{sqrt}(3) * \text{Ln}(\text{OR}) / \pi = 1.81 \text{ Ln}(\text{OR})$$

Then OR of 2.33 corresponds with SMD of 0.47, and OR of 2.85 corresponds with SMD of 0.58.

1. Chinn S. A simple method for converting an odds ratio to effect size for use in meta-analysis. *Stat Med* 2000;19(22):3127-31.
